In consultation with NCCIH program staff and the DSMB in 2022 we have outlined our planned publications for presenting our main results and have revised the primary statistical test that would be used to evaluate differences in mean outcomes across the treatment groups. Specifically, rather than conduct individual tests of SMT alone, SSM alone, and the combination against medical care with adoption of a multiple comparisons correction for three tests we will now use an overall test of equality across the four groups to conduct a single omnibus hypothesis test followed by the estimation of key group comparisons using Fishers least significant difference methods to construct individual nominal 95% confidence intervals with reporting of the induced simultaneous coverage. These methods will be used for primary analysis of the 3 primary effectiveness outcomes : LBP-Impact and pain and disability.

We plan to present principal findings in two key publications. The first publication would focus on average pain and disability over 1-year as the multiple primary outcomes and present recovery at 6-months (previously a primary outcome) as one of the secondary outcomes. A second paper will focus on LBP Impact averaged over months 10-12 as the primary outcome .

Modifications to Statistical Analysis Plan Regarding Primary Outcome

(edited July 2021)

In consultation with the NCCIH program staff and DSMB in the Spring of 2021 we have changed our primary outcome for assessment of treatment impacts on chronicity prevention. Specifically, we have replaced our original NIH Task Force on Research Standards for Chronic LBP (referred to as RTF) dichotomous chronicity measure with the RTF quantitative impact measure. The LBP-Impact outcome measure is a subset of the Promise 29 measures, **which is already being collected at baseline and every month during the follow-up year from the start of the trial**. As a secondary outcome measure, we will compare differences across treatment groups in the distribution of patients with mild, moderate, and severe impact.

Modifications to Statistical Analysis Plan in Response to COVID-19 Impacts

(edited August 2020)

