Effectiveness Hypothesis: We will focus on parallel analyses for pain and function. We hypothesize that SMT alone will decrease average pain by at least 1 point, and average disability by 2 points. Similarly, SSM alone will decrease average pain by at least 1 point, and average disability by 2 points, and the combination of SMT+SSM will lead to an sub-additive net decrease of <2 points and <4 points respectively.

Primary outcome variables: We will derive measure of disability and pain by calculating the time-averaged patient outcome using the monthly measurements taken over the year of follow-up.

Primary Analysis: For quantitative outcomes we will focus on analyses that generally do not assume that the effects of SMT and SSM are additive since we have adequate power to evaluate specific group contrasts. We will use linear regression methods with robust standard errors to test for the difference in mean scores comparing each intervention group to MC. Let Y_{ij} denote the outcome of interest (either average pain or average disability for parallel analyses). Similar to our primary analysis of LBP impact 1 we will use a linear regression model with robust standard errors using the structure:

$$\text{Four Groups Model: } E(Y_{ij} | X_{ij}) = \beta_0 + \beta_1 \cdot \text{Site}(2)_j + \beta_2 \cdot \text{RiskGroup}_{ij} + \beta_3 \cdot \text{SMT-Only}_{ij} + \beta_4 \cdot \text{SSM-Only}_{ij} + \beta_5 \cdot \text{SMT-and-SSM}_{ij} + \beta_6 \cdot \text{Period}(2)_{ij} + \beta_7 \cdot \text{Period}(3)_{ij}$$

In the primary regression model the parameters of interest are:

β_3 = adjusted mean difference comparing SMT Only to UMC;

β_4 = adjusted mean difference comparing SMT Only to UMC;

β_5 = adjusted mean difference comparing combined SMT and SSM to UMC.

This model considers each treatment group separately using an indicator of SMT only (*SMT-Only*), an indicator of SSM only (*SSM-Only*), and an indicator of combined therapy with both SMT and SSM (*SMT-and-SSM*). We will also add the baseline outcome as a covariate to perform a variation of ANCOVA for repeated measures.

Table 9.2: Power for the overall F-test of equality of means under various alternative scenarios.

Average pain intensity & disability over 12 months post-randomization (alpha = 0.05/2)

Alternative	SMT Alone	SSM Alone	SMT + SSM	Power
Additive	0.20	0.20	0.40	88%
Sub-Additive 1	0.25	0.25	0.35	85%
Sub-Additive 2	0.30	0.30	0.30	89%
Sub-Additive 3	0.25	0.25	0.25	74%

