Single effect 1a	0	0.30	0.30	96%
Single effect 1b	0.30	0	0.30	88%
Single effect 2a	0	0.25	0.25	83%
Single effect 2b	0.25	0	0.25	71%

Our primary analysis will test the global hypothesis that these three treatment comparisons are all null using a multivariate Wald test with 3 degrees of freedom and alpha=0.05/2 to account for the pair of primary outcomes (pain and disability). We will then provide individual confidence intervals for each coefficient that compares an intervention group to medical care based on Fishers least significant difference methods which provide individual nominal 95% confidence

intervals and also estimates the simultaneous coverage probability.

A secondary evaluation will consider whether the separate effects of SMT and SSM are potentially additive, and this will be done using a formal test for interaction:

$$\text{Interaction Model: } E(Y_{ij} | X_{ij}) = \beta_0 + \beta_1 \cdot \text{Site}(2)_j + \beta_2 \cdot \text{RiskGroup}_{ij} + \beta_3 \cdot \text{SMT}_{ij} + \beta_4 \cdot \text{SSM}_{ij} + \beta_5 \cdot \text{SMT}_{ij} \cdot \text{SSM}_{ij} + \beta_6 \cdot \text{Period}(2)_{ij} + \beta_7 \cdot \text{Period}(3)_{ij}$$

In this model a test of H0: $\beta_5=0$ allows us to determine if there is strong evidence for synergistic or antagonistic effects associated with combined treatment. Given that we evaluate interaction for both disability and pain we will use a Bonferroni corrected alpha of 0.05/2.

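### Do the nominal 95% arm-versus-MC intervals for pain and disability need a 0.05/2 adjustment, or a stated decision rule, to match the omnibus test?

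*Combined protocol and SAP*

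**What the plan says.** The modification to Section 9 on primary analysis and multiple comparisons (edited September 2022) drops separate corrected tests of SMT, SSM and the combination against MC. In their place it puts "a single omnibus hypothesis test followed by the estimation of key group comparisons using Fishers least significant difference methods", with individual nominal 95% intervals and a report of the simultaneous coverage they imply. Its scope is explicit: "These methods will be used for primary analysis of the 3 primary effectiveness outcomes : LBP-Impact and pain and disability". The text records that this was settled in consultation with NCCIH program staff and the DSMB.

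The section on primary effectiveness outcomes 2 and 3 carries this out. Each outcome has a "multivariate Wald test with 3 degrees of freedom and alpha=0.05/2 to account for the pair of primary outcomes (pain and disability"). The follow-up intervals are "based on Fishers least significant difference methods which provide individual nominal 95% confidence" intervals. The interaction test is also split: "Given that we evaluate interaction for both disability and pain we will use a Bonferroni corrected alpha of 0.05/2".

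Two sentences in that section sound different. The hypothesis is specific to an arm: "We hypothesize that SMT alone will decrease average pain by at least 1 point, and average disability by 2 points", with the same figures for SSM alone. The primary-analysis paragraph says linear regression will be used "to test for the difference in mean scores comparing each intervention group to MC". The LBP-Impact section has the same structure: arm-specific hypotheses, a 3-df omnibus test (at 0.05) and nominal 95% least-significant-difference intervals.

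**The concern.** The plan treats pain and disability as a pair that needs 0.05/2 at the omnibus and interaction tests, yet leaves the arm-versus-MC intervals at 95%. Those intervals are where a reader will look to learn which arm works, because a 3-df test cannot say. Fisher's least significant difference is also the name of a testing procedure, the hypotheses concern single arms, and one sentence speaks of testing each group against MC. No stated rule says how the arm-specific hypotheses will be judged.

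If an interval that excludes zero were reported as proof that an arm works, the two-outcome correction would not cover that claim. The omnibus gate gives no protection once another arm is truly effective: the omnibus then rejects because of that arm, and the ineffective arm's intervals are read at 5% each, twice.

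**Working it through.** **Inputs.** From the power text for LBP-Impact in Section 9: 1000 enrolled, 90% followed, about 300 each in MC and SSM and 200 each in SMT and SMT+SSM. That gives 270/270/180/180 evaluated. I place 180 per arm in the full-factorial periods and the extra 90 MC and 90 SSM in the restricted period, with period adjustment as planned. Effects are in SD units. The pain–disability correlation is not in the documents; I use 0 to 0.95.

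**Standard errors.**
- SSM versus MC: √(2/270) = 0.0861.
- SMT versus MC: the restricted period sharpens the MC mean through the SSM–MC difference. Its variance is (2/180 + 2/270)/4 = 0.00463. Adding 1/180 = 0.00556 for SMT gives 0.01019, so the SE is 0.1009. The combination has the same SE.

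**Reproducing Table 9.2.** Let V be the covariance matrix of the three coefficients. The noncentrality is λ = β′V⁻¹β, and power comes from the noncentral F with 3 numerator df at alpha 0.025.

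| Row | λ | Power, computed | Power, plan |
|---|---|---|---|
| Additive | 16.20 | 89.4% | 88% |
| Sub-additive 1 | 14.85 | 86.0% | 85% |
| Sub-additive 2 | 16.20 | 89.4% | 89% |
| Sub-additive 3 | 11.25 | 72.8% | 74% |
| Single effect 1a | 20.25 | 95.6% | 96% |
| Single effect 1b | 16.20 | 89.4% | 88% |
| Single effect 2a | 14.06 | 83.7% | 83% |
| Single effect 2b | 11.25 | 72.8% | 71% |

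All eight rows agree within 2 points, so the design is represented correctly.

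**Error rate if the intervals were tests.** If both omnibus tests are certain to reject and the outcomes are uncorrelated, one ineffective arm is flagged on at least one outcome with probability 1 − 0.95² = 9.75%. At correlation 0.95 this is 6.5%. Next I simulate each outcome's omnibus test (chi-square, 3 df, 0.025) followed by |z| > 1.960, with 400,000 draws per scenario:

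| Truth | Flagged on pain or disability, correlation 0 to 0.95 | One outcome alone |
|---|---|---|
| Row 1a (SMT ineffective) | 9.6% to 6.4% | about 5.0% |
| Row 1b (SSM ineffective) | 9.6% to 6.4% | about 4.9% |
| Row 2a (SMT ineffective) | 9.5% to 6.3% | about 4.9% |
| Row 2b (SSM ineffective) | 9.1% to 6.1% | about 4.6% |
| Only the combination works, 0.30 SD: either null arm flagged | 16.7% to 11.3% | about 8.8% |
| Only the combination works, 0.40 SD: either null arm flagged | 17.7% to 11.7% | about 9.2% |
| Global null: any arm flagged | 4.4% to 3.0% | about 2.2% |

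These are two-sided rates. False benefit alone is half: 3.0 to 4.9% in the four single-effect rows. The two combination-only rows are not in Table 9.2. The other four rows of Table 9.2 have no ineffective arm.

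**What 97.5% intervals would buy and cost.** The critical value rises from 1.960 to 2.241, so intervals widen by 2.241/1.960 − 1 = 14%. At the plan's SDs the SMT-versus-MC half-width goes from 1.96 × 0.1009 × 6.5 = 1.29 to 2.241 × 0.1009 × 6.5 = 1.47 RMDQ points, and from 0.59 to 0.68 NRS points (SD 3.0). The single-effect rows fall to 3.2 to 4.9%. With two ineffective arms at least one is still flagged 6 to 9% of the time. Power for SMT versus MC, after the omnibus rejects:

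| Scenario | 95% | 97.5% |
|---|---|---|
| 2 RMDQ points (0.308 SD), all arms effective | 83% | 77% |
| 1 NRS point (0.333 SD), all arms effective | 89% | 84% |
| Row 1b, 0.30 SD | 80% | 74% |
| Additive row, 0.20 SD | 50% | 39% |

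**Simultaneous coverage.** At nominal 95% it is about 87% for the three intervals of one outcome, and 76 to 84% for all six. The plan attaches the coverage statement to the coefficients of a model fitted separately to each outcome, so three is the natural count.

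**The case for a change.** The best case for a change is that one sentence costs nothing and would prevent a choice of reading after unblinding. The hypotheses are specific to an arm, the pain and disability text speaks of testing each group, and both outcomes go into one paper as its primary outcomes, so pooling across them is natural. The plan also never expressly makes the intervals conditional on the omnibus. Read as ungated tests under the global null, at least one of the six would exclude zero 16 to 24% of the time (100% minus the 76 to 84% coverage above).

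The wording mismatch stands: the testing phrase does not sit well with the 2022 modification. The rest does not carry the point. That modification states the role of the intervals and names pain and disability as covered, and the analysis text then tests only the global hypothesis before providing intervals. The ungated figure is the complement of a simultaneous coverage that the plan undertakes to report. A hypothesis of at least 1 point in pain or 2 in disability concerns size. Excluding zero would not settle it at either level, while an estimate with its interval addresses it directly. Nor is the mismatch peculiar to these two outcomes: LBP-Impact has the same kind of hypotheses and the same intervals.

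**Conclusion.** No change is needed. The arithmetic behind the worry is sound, but it describes a use of the intervals that the plan set aside when it replaced individual arm tests with one omnibus test and estimation. Used as stated, they are valid 95% intervals with simultaneous coverage disclosed. Stating again that they are estimates would alter no number and no power. Tightening them to 97.5% would override a choice made in consultation with the funder's staff and the DSMB. It would cost about 5 to 11 points of SMT-versus-MC power and still not give full control with two ineffective arms. Keeping 95% is a fair trade-off, and the phrase about testing each group is a slip that analysts can read in the light of the 2022 text.

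The 6 to 10% figure rests on four assumptions: the intervals are read as tests after that outcome's omnibus rejects, the two outcomes are pooled, exactly one arm is ineffective on both, and the correlation lies between 0 and 0.95. With two ineffective arms the corresponding figure is about 11 to 18%. For one ineffective arm on one outcome it is at most about 5%, and under the global null 3.0 to 4.5% over both outcomes. The SDs behind the power figures are the plan's own, which it calls conservative, so actual power may be higher at either level.

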Subgroup/Moderator Analyses: We will consider two pre-specified subgroup analyses to look at treatment effects within: subjects who are medium risk based on STarT Back, and subjects who are high risk; and subjects stratified based on their duration of LBP. Subgroup analyses will use logistic or linear regression among restricted subsets to quantify specific treatment effects, and formal evaluation of differences in treatment effects across subgroups will be conducted using treatment by subgroup interactions. In addition to the pre-specified subgroup analyses we will also conduct exploratory analyses to evaluate the heterogeneity of treatment effects according to Gender, Race, and Ethnicity.

Responder Analysis: We will focus on evaluation of a >50% improvement in pain or function from baseline to six months, and from baseline to one year. We will also consider a >30% improvement, and a comprehensive responder analysis that looks at the cumulative percentage of subject achieving a range of improvement percentages as described in Farrar, Dworkin, and Max.⁷⁶

Secondary Outcomes: We will assess secondary outcomes including the PROMIS-29 measure, productivity loss, healthcare utilization (e.g., opioid use, injection, MRIs), and AEs for the combined group (SMT+SSM) and each intervention alone relative to MC. We will use linear or logistic regression and the Four Group model structure given above and will use linear mixed models or generalized estimating equations (GEE) for longitudinal analysis of secondary outcomes.¹⁵⁴

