Longitudinal analyses of patient trajectories for pain and disability: We will use the monthly measures of disability and weekly measures of pain to conduct longitudinal analysis that characterizes the mean profile over time for each intervention group. Formal comparison of profiles will be based on linear mixed models or GEE. Furthermore, we will conduct exploratory analyses that assume latent classes with associated trajectories, and we can evaluate whether these groups differ across the intervention arms.¹⁵⁹ We have recently used these methods for analysis of the BOLD back pain cohort.¹⁶⁰

Longitudinal Analysis Adjusting for Concomitant/Subsequent Therapy: Our first analysis will be a descriptive summary of the types and frequency of additional treatments received throughout the study. The initial study intervention occurs within the first two months and outcomes are collected through one year. Therefore, there is potential for variation in the treatment received according to randomized group or non-study interventions during months 3-12. Intermediate treatment received is a post-randomization variable and potential intermediate outcome that will be considered in mediation analysis. In addition, we can use structural nested mean models (SNMMs) or marginal structural models ^{161 162} to adjust for time-varying confounding (treatment contamination) associated with intermediate treatment received. For example, if we consider longitudinal concomitant treatment a_k , measured at times $k=1, 2, \dots, m$, then using SNMM notation we can define the 1-year counterfactual outcome for subject i as $Y_i(Z, a_1, a_2, \dots, a_m)$ which represents the potential outcome associated with baseline treatment Z and time-varying concomitant treatments. We can use either SNMMs or MSMs to estimate population mean outcomes under controlled concomitant treatment paths such as the expected outcome with treatment Z and no additional longitudinal treatments: mean of $Y_i(Z, 0, 0, \dots, 0)$. For these longitudinal analyses we will use the monthly measured RMDQ and Pain NRS as the outcomes in parallel regression analyses. We have previously conducted critical evaluation of such methods for the analysis of surgical non-compliance.¹⁶³

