Missing data may include missing covariate information, study dropout, or missed and/or mistimed participant visits. While the PACBACK protocol includes procedures to ensure the most “complete” follow-up data on every enrolled participant, it is likely that some participants will have incomplete data. We will determine reasons for missingness, classifying each missingness pattern as missing completely at random (MCAR), missing at random (MAR), or missing not at random (MNAR). The MCAR mechanism occurs when the probability of response is independent of both the observed data and the unobserved data¹⁷⁰. All protocols will include recommended sensitivity analyses that will help determine the extent of potential biases that could affect the results.

In longitudinal analyses, likelihood-based analyses of complete-case data for the linear mixed-effects model, the generalized linear mixed-effects model, and the nonlinear mixed-effects model lead to valid inference under MCAR and MAR mechanisms, whereas the GEE analyses lead to valid inference only in the presence of MCAR mechanisms.^{170 171} Statistical tests to assess the validity of the MCAR assumption in certain circumstances are available, but they are model-dependent and non-robust.¹⁷²⁻¹⁷⁴ In general, we will advocate the use of multiple imputation (MI)¹⁷⁵ both to assess the sensitivity of results and to correct for bias from missing covariates. We will consider the missing data mechanism, analysis approach, and plausibility of the congeniality assumption.^{176 177} If MNAR data are suspected, there are three basic approaches to address this challenge, namely, (1) selection models¹⁷⁸⁻¹⁸⁰, (2) pattern-mixture models^{181 182} and (3) MI.^{175 183} We recommend MI because it appears to be more robust. We can apply MI using weights dependent on the probability of dropout to assess the dependence of results on dropout.

We will also consider selection models with varying dropout parameters in sensitivity analyses.^{183 184}

Potential Problems & Alternative Strategies:

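### Longitudinal secondary and trajectory analyses may use GEE without weights or a rule for choosing it, although the plan says GEE needs MCAR; the plan also credits MAR validity to complete-case mixed models

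*Combined protocol and SAP*

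**What the plan says.** Three parts of section 9 bear on this point.

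- **Secondary Outcomes.** For PROMIS-29, productivity loss, healthcare utilization and adverse events, the plan "will use linear mixed models or generalized estimating equations (GEE) for longitudinal analysis of secondary outcomes".
- **Longitudinal analyses of patient trajectories for pain and disability.** "Formal comparison of profiles will be based on linear mixed models or GEE".
- **General Missing Data Considerations.** This section says that "likelihood-based analyses of complete-case data for the linear mixed-effects model", and for the generalized linear and nonlinear versions, "lead to valid inference under MCAR and MAR mechanisms", "whereas the GEE analyses lead to valid inference only in the presence of MCAR mechanisms". Of statistical tests of MCAR it says that "they are model-dependent and non-robust".

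The same section advocates multiple imputation in general terms, "both to assess the sensitivity of results and to correct for bias from missing covariates", and prefers it if MNAR is suspected. Dropout weights appear as an optional variant of multiple imputation, and selection models are to be considered in sensitivity analyses. No weights are attached to the GEE, and no working correlation is named.

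**The concern.** The plan leaves open a method whose validity condition, by its own account, is narrow and cannot be checked reliably. GEE is the natural route for the binary and count outcomes (opioid use, injections, MRIs, adverse events), because the only mixed model offered under Secondary Outcomes is linear. For the pain and disability trajectories, both quantitative, nothing decides between the two methods.

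The wording on mixed models is a second problem. Likelihood methods keep their validity under MAR when every observed value enters the model. Restricting the data to participants with complete series generally loses that property. Taken literally, the sentence would make the better of the two routes no safer than the other.

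At stake are the late contrasts in the secondary and trajectory analyses. Outcome-related dropout that differs by arm is plausible here: participants are unblinded (section 3.5), expected visit numbers differ by arm (section 5.4), and lack of response or worsening is a listed reason for stopping the intervention (section 8).

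**Working it through.** **Plan figures.** The plan gives no figure for missing-data bias. Its follow-up figures are 90% (power text for LBP Impact), at least 88% at one year (power text for chronicity) and a target of 85% or higher for each monthly survey (section 10.3.3). Losses are therefore 10%, 12% and 15%. As a check on the first, a noncentral F calculation adjusted for period used 180 evaluated in each of four arms plus 90 each in MC and SSM from the restricted period: 4 × 180 + 2 × 90 = 900. It gives 93.6% for the Sub-Additive 2 row of Table 9.1, against 94% stated. This confirms the 10% loss in the design; the bias argument does not depend on it.

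**Why the bias can arise.** Unweighted GEE with working independence and a separate mean for each arm and month returns the observed-case mean. Its error in arm a at month k is E(Y | observed) − E(Y). The error in the contrast is the difference between the two arms' errors, so it cancels when dropout selects equally in both.

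**Simulation inputs.**
- From the plan: RMDQ SD 6.5 and a true difference of −2.0 points (power text for outcomes 2 and 3); month-12 dropout of 12% or 15%.
- Assumed, not in the documents: the same difference at all 12 months; two correlation structures (A: exchangeable plus autoregressive; B: autoregressive at 0.9 per month); monotone MAR dropout with a log-odds slope of 0.5 per SD of the last score; equal total dropout in both arms; no covariates; 400,000 participants per arm.
- Dependence on score: the same in both arms, in one arm only, or opposite in the two arms.

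Each GEE or mixed-model estimate solves Σ Xᵢ′Vᵢ⁻¹(Yᵢ − Xᵢμ) = 0 over the observed months. V is the identity (independence), exchangeable at the average correlation, or the true covariance (standing for a correctly specified likelihood mixed model on all available data). The Monte Carlo standard error of a full-data difference is 6.5 × √(2/400,000) ≈ 0.015.

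**Month-12 RMDQ difference.**

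| Dependence | Structure, dropout | Full data | Independence GEE = complete case | Exchangeable GEE | Mixed model, all available |
|---|---|---|---|---|---|
| Same | A, 12% | −2.01 | −2.01 | −2.01 | −2.01 |
| Same | A, 15% | −2.00 | −1.99 | −2.00 | −1.99 |
| Same | B, 12% | −1.97 | −1.97 | −1.97 | −1.97 |
| Same | B, 15% | −2.00 | −1.99 | −1.99 | −1.99 |
| One arm | A, 12% | −2.00 | −1.72 | −2.02 | −2.00 |
| One arm | A, 15% | −2.01 | −1.67 | −2.05 | −2.02 |
| One arm | B, 12% | −1.99 | −1.76 | −2.04 | −1.99 |
| One arm | B, 15% | −1.98 | −1.70 | −2.04 | −1.98 |
| Opposite | A, 12% | −2.01 | −1.45 | −2.06 | −2.01 |
| Opposite | A, 15% | −1.99 | −1.30 | −2.06 | −2.00 |
| Opposite | B, 12% | −1.99 | −1.53 | −2.10 | −1.99 |
| Opposite | B, 15% | −2.01 | −1.44 | −2.15 | −2.02 |

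Independence GEE and complete-case analysis agree at month 12 by construction: under monotone dropout, those observed at month 12 are the completers.

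**Sizes in SD.**
- Smallest bias under unequal dependence: (1.99 − 1.76)/6.5 = 0.23/6.5 ≈ 0.04 SD, or 0.23/1.99 ≈ 12% of the effect.
- Largest: (1.99 − 1.30)/6.5 = 0.69/6.5 ≈ 0.11 SD, or 0.69/1.99 ≈ 35% of the effect.
- Exchangeable GEE, largest: (2.15 − 2.01)/6.5 = 0.14/6.5 ≈ 0.02 SD, away from the null.
- Mixed model on all available data: within 0.01 point of the full-data value in every row.

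Inverse-probability-weighted GEE and 10% loss were not simulated.

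**The case against.** The strongest reply is that the size depends on choices that the documents do not make. No working correlation is specified, and an exchangeable one nearly removes the bias. The dropout pattern must also differ by arm, which the documents do not say. Both points stand, and both limit the size of the claim. They also show why the method should be named: the silence leaves room for the biased version.

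A second reply is that the complete-case phrase is loose wording in generic text. Section 3.1 lists use of all data in an intention-to-treat analysis, and the trajectory paragraph draws on all the weekly and monthly measures. This reading is quite possible. If it is right, that half of the point is a wording correction.

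A third is that the choice may simply follow outcome type, with mixed models for scores and GEE for binary and count data. That is sensible for the secondary outcomes, but the plan does not say it, and it cannot explain the choice offered for pain and disability.

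A fourth is that the plan does address missing data. It does, and a reader should not infer that nothing is planned. But multiple imputation and selection models are described for sensitivity, for missing covariates or for suspected MNAR. None is made the main handling of missing longitudinal outcomes. That the GEE is unweighted is an inference from the plan's silence on weights.

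Finally, section 10.3.3 keeps the month-12 survey after other surveys are switched off. This may make real month-12 loss less monotone than in the simulation.

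**Conclusion.** The point holds as a modest defect of specification. The plan permits GEE without weights for longitudinal secondary outcomes and trajectories while stating that GEE needs MCAR, and it assigns MAR validity to the wrong data set. Under the assumed scenarios the month-12 RMDQ contrast can be off by about 0.04-0.11 SD with working-independence GEE or a literal complete-case analysis. This requires dropout that depends on outcome differently by arm. The slope, correlation structures and dropout patterns are assumptions, so the range is illustrative.

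Three stronger readings are not supported. A reader might infer that the plan expects MCAR or MAR to fail; it says only that missingness patterns will be classified. A reader might infer that any GEE would be badly biased; the equal-dependence and exchangeable results show otherwise. A reader might extend the point to the main results; the three primary analyses are linear regressions on patient-level averages and use neither method.

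**What to change.** Make three changes in section 9:

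1. Under Secondary Outcomes and the trajectory analyses, name likelihood mixed models on all available observations as the main method for quantitative longitudinal outcomes.
2. For binary and count longitudinal outcomes, specify inverse-probability-weighted GEE, or GEE after multiple imputation of the missing outcomes.
3. Under General Missing Data Considerations, replace complete-case data with all available data.

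The cost is a few lines of text plus a dropout or imputation model for the binary and count outcomes, whose predictors should be stated in advance. No new data are needed. These methods rest on MAR, so the planned sensitivity analyses for MNAR should stay.
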